5.1 Secondary Endpoint

Secondary endpoints include:

- Baseline differences in MCC in non-smokers/non-vapers as compared to e-cigarette users
- Differential cell counts in CA-induced changes in IS samples.
- Regional lung clearance rates via MCC scan.

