No carryover effects. It is important to note that the 2-treatment, 2-period, 2-sequence crossover design, CO (2,2,2), is incapable of coping with differential carryover effects and is being used in this study only because we are absolutely confident in our assumption that the carryover effects (λ_A and λ_B) are zero in the target population. If this assumption is incorrect, then the results of the study will be biased. The CO (2,2,2) design provides very poor precision for estimation of differential carryover effect ($\lambda_A - \lambda_B$). Any test of the null hypothesis, "($\lambda_A - \lambda_B$) = 0", will have very little power in this study.

No tests for carryover effects. A two-stage testing procedure will not be used. (e.g., a test for differential carryover is performed first, and if the test is not statistically significant then the data from both periods are used; else, estimates are obtained excluding period-2 data.) That strategy performs poorly in terms of bias, precision and power, and may yield misleading results. If it is plausible that differential carryover effects may exist in the target population, then the best approach is to employ a sufficiently longer washout interval, or use a study design that can account for carryover effects.

Models for immune cell measures. In Stage 2, for immune cell measures obtained via sputum induction (IS) immediately after and 48hrs after each vaping session, the dependent variable in the linear mixed-effects model will be the post-vaping change-from-baseline value. The model is:

 $E[\ \Delta Y_{ij}(t) \ | \ \underline{X} \ , \ Y_{ij}(t_0) \] \ = \ \ \mu_A \ X_1 \ + \ \ \mu_B \ X_2 \ \ + \ \ \delta_A \ X_3 \ \ + \ \ \delta_B \ X_4 \ \ + \ \ \pi \ X_5 \ \ + \ \ \epsilon_{ij}(t)$

Entries ar	e expected value		Treatment Sequence	
		A:B		B:A
Period 1		μ A		μ _B
Period 2	at 0 hrs	$\mu_{\rm B} + \pi$		$\mu_A + \pi$
Period 2	at 48 hrs	$\mu_{\rm B} + \delta_{\rm H}$	$\underline{a} + \pi$	$\mu_{\underline{A}} + \delta_{\underline{A}} + \pi$

Transformations. Based on prior publications and previous experience with of the outcome measures of interest, some of the measures are known to follow distributions that are skewed or otherwise not well approximated by Gaussian distributions. Appropriate transformations of those outcome measures will be identified and applied prior to analysis of the data.

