5.4 Sample Size and Power Sample size for MCC: In a study of healthy subjects (n=12), using the same methods described here, we found a standard deviation of the delta between 2 repeat MCC measures of 7 % (SD) in average clearance through 90 minutes (Ave90Clr) (i.e. the average of %clearance ((1-retention) X100) over all 10 min data points from 10-90 min) (Bennett et al 2015). In the same study these healthy subjects were challenged with 7% hypertonic saline in a repeated, crossover design, and we observed a decrease from 16% to 12% Ave90Clr 4 hours after HS treatment compared to baseline (no HS). In another recent study, again using the same MCC methods described here, we found that endotoxin (LPS) challenge in mild asthmatics (n=15) resulted in a slowing of MCC from 19% to 14% Ave90Clr 4 hours post LPS challenge compared to baseline. The primary endpoint/comparison for the current study will be CA e-liquid induced changes in MCC as compared to the baseline MCC measurement (paired comparison). Secondarily the vehicle itself (PG/VG mix without CA, or nicotine contained in the e-liquids) may also modify MCC without CA (also a simple paired comparison). In other words, the e-cigarette without CA may be an active vehicle, not an inactive placebo. If e-liquids with or without CA decrease MCC similarly to either 4 hour post HS or LPS, using an estimated SD of 7.0 % for repeat measures, a decrement of 4.5 % in Ave90Clr (or a 30 % decrement in MCC) may be seen with **n=20** volunteers (β = 0.80 and α =0.05). Based on our in-vitro findings where cilia

were completely immobilized in normal human airway cells for 60 minutes following CA administration, we think the 4.5% reduction in Ave90Clr is likely an underestimate of the anticipated CA-liquid effect. We anticipate a 10% incompletion/drop out rate, which will be addressed by aiming to enroll n=22 subjects into the study.

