The calculated power for the MCC comparison between vapers (e-liquid users) and non-vapers (healthy adult nonsmokers) will be based on the baseline MCC in n=20 for the former and n=32 for the latter (12 subjects studied recently in Bennett et al 2015 and an additional 20 non-vaping subjects here). The proposed difference in MCC (Ave90Clr) between the two groups is 4.5%, a chronic effect similar to the acute hypothesis above and $\frac{1}{2}$ of the relative difference seen between healthy adults and patients with chronic bronchitis with FEV1<40% pred (Anderson et al). From Bennett et al (2015) the mean baseline for health nonsmoking adults was 16% (+/-6). To observe the 4.5% absolute difference between the two groups we will have a power of 0.75 with a type I error of 0.05. It is unlikely that we will observe the 4.5% change both acutely (discussed above) and chronically, i.e. chronic effects of CA in vapers may mask the effect of a single dose of CA or the baseline MCC may be normal in vapers but slow with each acute dose of CA e-liquids. Studying both the single dose effect within the vapers (repeat comparisons) and the baseline differences between vapers and non-vapers (group comparison) will allow for a more complete picture of e-cigarette effects on MCC. These are the first studies to assess the effect of e-cigarettes on MCC in healthy adult subjects.

To assure that we would have sufficient power to determine statistically significant differences in IS cells in the proposed studies, we used preliminary data obtained from SI immune cells from non-vaping controls and e-cigarette users. In this study, the mean percentage of macrophages with high inflammatory markers in non-smokers was 20.8 with a standard deviation of 24.66. Assuming a difference between baseline and treatment group to be a 2-fold increase in percent macrophages with high inflammatory markers, which we saw in samples obtained from e-cigarette users, we will have a power of 0.965 with a type I error of 0.05 using the sample size of n=20 determined for MCC above.

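### The 0.965 power for sputum macrophages uses a between-subject SD in non-smokers, and an apparent user versus non-user difference, as if both described change within vapers

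*Combined protocol and SAP*

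**What the plan says.** Section 5.4 introduces the sputum calculation as assurance of sufficient power. It draws on preliminary sputum data from non-vaping controls and e-cigarette users, and reports that "the mean percentage of macrophages with high inflammatory markers in non-smokers was 20.8 with a standard deviation of 24.66". It then assumes a 2-fold increase between baseline and treatment group, "which we saw in samples obtained from e-cigarette users", and concludes that "we will have a power of 0.965 with a type I error of 0.05 using the sample size of n=20 determined for MCC above". It does not state the test, the sidedness, an SD of paired change or a within-subject correlation.

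The Stage 2 model for sputum immune cells in section 5.3 is a within-vaper analysis: "the dependent variable in the linear mixed-effects model will be the post-vaping change-from-baseline value". The same section notes that "some of the measures are known to follow distributions that are skewed or otherwise not well approximated by Gaussian distributions" and plans transformations.

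For MCC, section 5.4 keeps two kinds of SD apart. The paired calculation uses the SD of repeat differences ("we found a standard deviation of the delta between 2 repeat MCC measures of 7", in percent). The vaper versus non-vaper calculation uses the spread of 6 across healthy non-smoking adults.

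**The concern.** Power for a change from baseline depends on the SD of paired differences and on the size of the acute change. The sputum paragraph gives neither. Its SD is a spread across non-smokers. Its effect appears to be a contrast between two groups of people, and no before-and-after vaping data are described. For MCC, section 5.4 itself separates chronic from acute effects and warns that one may mask the other; the sputum calculation does not make that separation.

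The 0.965 is the only power figure offered for sputum cells, and Aim 2b concerns the effect of CA on them. No sputum power is given for the randomised CA versus no-CA contrast. Section 5.3 reports non-significant results as inconclusive, so a reader who trusts an unconditional 0.965 may misjudge what an inconclusive sputum result means.

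**Working it through.** **Inputs (section 5.4).** Mean 20.8 and SD 24.66 in non-smokers; a 2-fold increase, so a difference of 41.6 − 20.8 = 20.8 points; n = 20; alpha 0.05 (two-sided assumed). MCC: SD of repeat difference 7; SD across subjects 6; difference 4.5; groups of 20 and 32.

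**1. Reproduce the stated figure.** Paired normal approximation, power = Φ(δ/(SD/√n) − 1.96):

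- 24.66/√20 = 5.514, and 20.8/5.514 = 3.772.
- Φ(3.772 − 1.960) = 0.965, as stated. The paired t version (19 df) gives 0.947.

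So 24.66 was used as the SD of the paired change.

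**2. What that assumes.** With equal variances, SD of difference = 24.66 × √(2(1 − ρ)). This equals 24.66 only when ρ = 0.5.

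**3. Vary the correlation** (δ = 20.8, n = 20, equal SDs; the correlations are assumptions):

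| ρ | SD of difference | Paired t power |
|---|---|---|
| 0 | 34.87 | 0.716 |
| 0.2 | 31.19 | 0.807 |
| 0.5 | 24.66 | 0.947 |
| 0.7 | 19.10 | 0.996 |

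**4. The plan's own MCC figures.** That 6 is a between-subject SD is confirmed by the group power: 4.5/(6 × √(1/20 + 1/32)) = 2.63, and Φ(2.63 − 1.96) = 0.75, as stated. The ratio of the two SDs is 7/6 = 1.17, which implies ρ = 1 − 49/(2 × 36) = 0.32. If sputum repeated like MCC (assumption), the SD of change would be 24.66 × 7/6 = 28.77, and paired t power at n = 20 would be 0.866.

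**5. Vary the effect** (SD of difference held at 24.66; the effects are assumptions):

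- 0.75 × 20.8 = 15.6 points: paired t power 0.765.
- 0.5 × 20.8 = 10.4 points: paired t power 0.433.

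**6. Read as a user versus non-user comparison** (δ = 20.8, common SD 24.66 assumed, two-sample t):

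| Group sizes | t power |
|---|---|
| 20 v 20 | 0.739 |
| 22 v 22 | 0.780 |
| 20 v 32 | 0.827 |

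The normal approximation gives 0.760 for 20 v 20 and 0.841 for 20 v 32. None of these is 0.965.

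**7. Scale.** SD/mean = 24.66/20.8 = 1.19 for a percentage that cannot fall below 0. This suggests skew, yet the power was computed on the untransformed scale.

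**The case against.** The strongest defence is that the arithmetic is right and the claim of sufficient power may survive. With the 20.8-point effect and equal SDs, t power is above 0.80 from a correlation of about 0.2 upwards, and it exceeds 0.965 when the correlation is high. Even the MCC-based figure is 0.87. This stands: the direction of any error is unknown, and the figure cannot be called overstated.

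The wording about the 2-fold increase is ambiguous. The terms baseline and treatment group could describe a before-and-after comparison in users, and the preliminary data are not in the document. This also stands, so the point about the effect is less certain than the point about the SD. The SD problem remains on either reading.

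The MCC ratio is a weak guide to sputum. It comes from rounded SDs in a study of 12 subjects. An approximate 95% interval for a correlation of 0.32 with n = 12 is −0.31 to 0.76, which includes 0.5. Nothing links the repeatability of tracer clearance to that of sputum flow cytometry. The 0.87 is an illustration and does not show that 0.5 is wrong.

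Finally, little depends on the figure. The secondary sputum endpoint in section 5.1 is "Differential cell counts in CA-induced changes in IS samples", this macrophage percentage is not named in sections 5.1 or 5.2, and MCC set n = 20. That limits the consequence but does not justify the number.

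**Conclusion.** The concern holds. As written, 0.965 is a conditional figure presented without its conditions: an SD of within-vaper change of 24.66 (correlation 0.5 if variances are equal) and an acute shift of 20.8 points. The document supports neither. If the first condition is relaxed over correlations of 0 to 0.7 with equal SDs, t power runs from 0.72 to 0.996. If instead the effect is halved with the SD of change at 24.66, it is 0.43. These ranges rest on assumed correlations, effects and equal SDs, and on a single paired t comparison. No single corrected value can be derived. The consequence is confined to the stated power for a non-primary sputum measure; the sample size is unaffected.

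**What to change.** In section 5.4, withdraw 0.965 as an unconditional Stage 2 power. State the test and sidedness, and restate t-based power at n = 20 for change from baseline. Use an SD of paired differences and a justified acute effect, on the scale to be analysed.

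If those inputs are not available, give a short table over labelled correlations and effects, as in steps 3 and 5 above. Note there that a single paired t only approximates the section 5.3 model, which has two post-vaping samples per session. Say also that no sputum power is claimed for the randomised CA versus no-CA contrast, or supply one.

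If the 2-fold user versus non-user difference is kept, attach it to the Stage 1 comparison. By t with equal SDs (assumption), power is about 0.74 at 20 v 20 and 0.78 at 22 v 22. It is 0.83 at 20 v 32, but only if the 12 earlier controls have this sputum measure.

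The cost is one reworded paragraph and a conditional power statement in place of a single figure. Sample size, design and procedures do not change.

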5.5 Interim Analysis

There is no interim analysis planned.

6 STUDY INTERVENTION (drug, device or other intervention details)

- **Description** The vape device e-liquids will be purchased by the research team, and maintained in a locked file cabinet in the CEMALB. The device will be loaded by study personnel, and the actual vaping session (as previously described) will occur in a supervised area of the CEMALB.

- **Receipt/Storage:** The device and the e-liquids are commercially available and will be purchased by study staff. These items will be stored in a secure area of the CEMALB.

- **Packaging/Labeling:** There will be no labeling attached at study visits. Study staff will log the e-liquid and device use.

- **Dosing** E-liquid with and without CA; tailored to the subjects current nicotine use.

- Treatment compliance and Adherence: Subjects will be monitored in real time as the use the vaping devices.

- Drug Return/Destruction: NA
- Drug Accountability: NA.

- **Radioisotope (Tc99m-SC):** Radiolabeled (Tc99m) sulfur colloid (SC) is prepared using TechneScan SC Kits (Mallinckrodt Medical) with binding efficiencies of greater than 98%. The solution of Tc99m-SC will be

obtained from the radiopharmacy in the Nuclear Medicine Section of the Department of Radiology or from the local Cardinal Health pharmacy.

7 STUDY INTERVENTION ADMINISTRATION(if applicable)

Randomization procedures: Randomization scheme will be generated by using the Web site Randomization.com (http://www.randomization.com) and provided to the study team. An individual not actively involved in the study will maintain the randomization scheme to assure blinding all personnel involved in the study. This individual will assign treatment Regimen A and B and will also be responsible for loading the e-cig with the appropriate solution for that session.

Blinding procedures: The study device will be loaded based on the randomization scheme by CEMALB personnel who are not directly involved in the study procedures or sample analyses to maintain blinding. Logs will be kept to document the order of the e-liquid sessions to assure adherence to the randomization scheme.

Unblinding procedures: Logs will be maintained with e-liquid dispensation, in a secure area. Unblinding will occur prior to data analysis only if there is a medical need.

8 SAFETY MANAGEMENT

-Adverse Event/Serious Adverse Event monitoring procedures Adverse and unplanned events will be assessed at each visits. AE's will be graded per the CTCAE.

- Adverse Event/Serious Adverse Event reporting procedures AE's and UP's will be reported to the IRB using the SOP provided by the IRB. The funding agency will be notified of any SAEs.

-Medical Emergency procedures? The most likely medical emergency would be bronchospasm associated with sputum induction. Albuterol is readily available for rescue treatment if needed, and epinephrine available. There is a code cart in the CEMALB. If more treatment is required, local EMS will be called for transport to UNC Hospitals ED.

-Data Safety Monitoring Plan? Safety is monitored in real time during the study sessions. The PI and a study physician will be notified of any subject safety concerns.

9 DATA COLLECTION AND MANAGMENT

-Monitoring Plan? Data will be entered into REDCap, which is designed for PI investigator-initiated studies such as this one. The PI, [name], will be responsible for data management.

-Case report forms? Case report forms will be developed by the study team, using templates from previous studies.

-How will confidentiality be maintained? All paper documents will be maintained by the study staff, and kept in a secure location when not in use.

10 RECRUITMENT STRATEGY: Subjects will be recruited from the existing database at the CEMALB (IRB #98-0799) as well as by mass emails, public advertisements, and the Join the Conquest Website.

11 CONSENT PROCESS

Describe the procedure that will be used to obtain informed consent/HIPAA authorization and assent (if applicable). The study will be described in detail to the subject, including why the study is being conducted, the medication being studies, the risks and benefits, and what is expected of the subject. The subject will be

given adequate time to read the consent, and consent will be obtained prior to any study procedures. We will not seek HIPAA authorization.

-Who will obtain consent/assent? Consent will be obtained by a study coordinator or a study investigator.

-Where will consent /assent process take place? The consent will take place at the UNC CEMALB, located in the Human Studies Facility of the US EPA on [name] in Chapel Hill.

-How will investigator assure that subjects comprehend the nature of the study, procedures, the risks and benefits? The subject will be encouraged to ask question regarding the study and procedures. Open ended questions will be asked of the subject to solicit correct responses, to help ensure that the subject understands the study commitment, procedures and risks and benefits.

